444 certified orthoptist.
 - 445 • Record the break and recovery points.
- 446 9. Convergence Amplitude Testing: Measured at distance (6 meters) using the PEDIG-approved
447 prism bar as described in the *IXT7 Procedures Manual*
- 448 • Testing must be performed by a pediatric ophthalmologist, pediatric optometrist, or
449 certified orthoptist.
- 450 10. Control of the Exodeviation #2 (repeat) (*see item #7*).
- 451 11. Ocular Alignment Testing:
- 452 • Testing must be performed by a pediatric ophthalmologist, pediatric optometrist, or
453 certified orthoptist.
 - 454 • Ocular alignment will be assessed by the cover/uncover test, simultaneous prism and
455 cover test (SPCT), and prism and alternate cover test (PACT) in primary gaze at
456 distance (3 meters) and near (1/3 meter) as described in the *IXT7 Procedures Manual*.
- 457 12. Control of the Exodeviation #3 (repeat) (*see item #7*)
- 458 13. Suppression: Assessment of suppression at distance (6 meters) using the Office Suppression
459 Test⁵⁹ as described in the *IXT7 Procedures Manual*
- 460 • Testing must be performed by a pediatric ophthalmologist, pediatric optometrist, or
461 certified orthoptist.
- 462 14. Retinal Correspondence (children 6 to <9 years only): Assessment of retinal correspondence
463 will be made when aligned and also when tropic using the Hering-Bielschowsky After Image
464 Test⁶⁰ as described in the *IXT7 Procedures Manual* using the PEDIG-supplied flash unit.
- 465 • Testing must be performed by a pediatric ophthalmologist, pediatric optometrist, or
466 certified orthoptist.
- 467

468 **2.5 Randomization**

469 Eligible participants will be randomly assigned on the study website to the following treatment:

470

- 471 1. Observation for 3 months – no treatment other than refractive correction
472 2. Full-time patching (all waking hours) for 3 months (right eye on even days, left eye on odd
473 days), in addition to refractive correction

474

475 The Jaeb Center will construct a Master Randomization List stratified by mean distance control
476 score at enrollment (2 to <3, 3 to <4, 4 to 5). A participant is officially randomized when the
477 website randomization process is completed.

478 **2.5.1 Observation Group**

479 Participants randomized to observation alone will not be allowed to receive any other treatment
480 for IXT, except refractive correction, for 3 months.

481 **2.5.2 Full-Time Patching Group**

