3.3.1 Masked Examiner

517 The masked examiner must be a pediatric optometrist, pediatric ophthalmologist, or certified
518 orthoptist who is not aware of the participant's assigned treatment. Because the enrolling
519 investigator will be unmasked to treatment group, they will not be allowed to serve as their own
520 masked examiner.

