604 distance (6 meters) and at near (33 cm) as outlined in the *IXT7 Procedures Manual*. The
605 examiner will be required to be masked to treatment group. Testing time is approximately 2-
606 4 minutes.
- 607 4. Cycloplegic Refraction: A cycloplegic refraction will be done prior to enrollment and only if
608 clinically indicated thereafter. After administration of eye drops, it typically takes 30 minutes
609 to achieve cycloplegia, and testing time for refraction of both eyes is in the range of 2 to 10
610 minutes.
- 611 5. Suppression Testing: Suppression will be assessed using the Office Suppression Test which
612 grades the level of suppression while tropic on a 4-level scale. Testing will be performed at 6
613 meters as outlined in the *IXT7 Procedures Manual*. Testing must be performed by a pediatric
614 ophthalmologist, pediatric optometrist, or certified orthoptist. The examiner will be required
615 to be masked to treatment group. Testing time is approximately 3-5 minutes.
- 616 6. Retinal Correspondence Testing: In children 6, 7, or 8 years old at time of randomization,
617 retinal correspondence status will be assessed by the Hering-Bielschowsky after-image test,
618 using a PEDIG-provided flash unit. Correspondence will be assessed when aligned and when
619 tropic to record overall status as either:

620 Testing must be performed by a pediatric ophthalmologist, pediatric optometrist, or certified
 621 orthoptist as outlined in the *IXT7 Procedures Manual*. The examiner will be required to be
 622 masked to treatment group. Testing time is approximately 3-5 minutes.

623

624 7. Control of IXT: Assessment of IXT control will be performed using the Office Control
 625 Scale³⁵ at both distance (6 meters) and near (1/3 meter), fixating an accommodative target.
 626 Testing must be performed by a pediatric ophthalmologist, pediatric optometrist, or certified
 627 orthoptist as outlined in the *IXT7 Procedures Manual*. The examiner will be required to be
 628 masked to treatment group. Testing time is approximately 3-5 minutes.

629 The scale below applies to both distance and near test distance separately.

630 Intermittent Exotropia Control Scale

631 5 = Constant Exotropia

632 4 = Exotropia > 50% of the 30-second period before dissociation

633 3 = Exotropia < 50% of the 30-second period before dissociation

634 2 = No exotropia unless dissociated, recovers in >5 seconds

635 1 = No exotropia unless dissociated, recovers in 1-5 seconds

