7.3 Sample Size

Sample size estimation is based on data from our previous IXT2 randomized trial comparing observation versus part-time patching for intermittent exotropia, limited to 278 participants with similar baseline age (3 to <9 years) and baseline control score at distance (2 or higher).²² Data are summarized in Table 1 below.

845 **Table 1 – Previous IXT2 Randomized Trial Data in 3- to <9-Year-Olds with IXT***

	Cohort	
	IXT2 Glasses Alone (Observation)	IXT2 Part-time Patching (3 hours/Day)
Distance Control Scores**		
Baseline		
n	147	131
Mean (SD)	2.88 (1.01)	2.93 (1.00)
3-Month Score		
n	131	116
Mean Score (SD)	2.59 (1.35)	2.15 (1.23)
95% CI for Mean Score	2.35 to 2.82	1.92 to 2.37
95% CI for SD Score	1.21 to 1.54	1.09 to 1.41
3-Month Change from Baseline		
n	131	116
Mean Change (SD)	0.30 (1.23)	0.78 (1.38)
95% CI for Mean Change	0.09 to 0.51	0.53 to 1.04
95% CI for SD Change	1.09 to 1.40	1.22 to 1.59

846 *Participants aged 3 to <9 years old with baseline distance control score of 2 or higher (worse).

847 ** A single measure of control was obtained at each visit in the IXT2 study.

848
849

850 In IXT2, after 3 months of observation versus treatment with 3 hours per day patching, the
851 observation group had a mean change based upon a single measure of distance control of 0.30
852 points (95% CI, 0.09 to 0.51 points) with a standard deviation of 1.23 points (95% CI, 1.09 to
853 1.40 points); and the 3 hours per day patching group had a mean change based upon a single
854 measure of distance control of 0.78 points (95% CI, 0.53 to 1.04 points) with a standard
855 deviation of 1.38 points (95% CI, 1.22 to 1.59 points); group difference patching – observation =
856 0.49 (95% CI 0.16 to 0.81). The correlation between distance control score at baseline and
857 change from baseline after 3 months was R=0.39 (95% CI, 0.27 to 0.48).

858 We are aware of no previous data on distance control score among children with IXT treated
859 with full-time patching. In our IXT5 study, after 6 months of treatment with overminus
860 spectacles, the mean change in distance control was 1.40 points (95% CI, 1.18 to 1.63 points)
861 with a standard deviation of 1.48 points (95% CI, 1.34 to 1.66 points). There was no 3-month
862 outcome in the IXT5 study; however, in the IXT3 pilot study, those treated with overminus
863 spectacles improved on average 1.2 points (95% CI, 0.5 to 1.9 points) with a standard deviation

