- 922 • Repeat the above sensitivity analysis using observed data from participants who completed
- 923 the 3-month visit within the protocol window (\pm 2 weeks).

924
 925 Sensitivity Analysis #3 (ITT minus participants with IOD 2 logMAR lines at enrollment):

- 926 • The overall number of participants with an interocular difference in distance VA of 2
- 927 logMAR lines (10 letters on E-ETDRS for patients \geq 7 years old) will be limited to 14.
- 928 • The ITT analyses as described in 7.5 will be repeated excluding these participants.

929
 930 **7.7 Analysis of the Secondary Endpoints**

931 All secondary analyses described below will use observed data only. Treatment group
 932 comparisons specified in the sections below will be controlled using false discovery rate (FDR)
 933 at the 5% probability level to account for the multiple outcomes. For all secondary analyses, an
 934 estimate of difference between the groups will be reported at each timepoint along with an FDR-
 935 adjusted confidence interval and p-value unless otherwise specified. Further details about the
 936 secondary analyses below will be part of a separate statistical analysis plan (SAP).

937 **7.7.1 Near Control**

938 At 3 months, near control will be evaluated similarly to the distance control primary analysis
 939 (section 7.6) using ANCOVA models that adjust for the mean near control score at baseline and
 940 the near angle by PACT at baseline.

941 Additionally, the proportion of participants with 2 or more points improvement in control from
 942 baseline will be compared between the treatment groups at 3 months using a two-sided Barnard's
 943 test with calculation of a two-sided FDR-adjusted confidence interval on the difference in
 944 proportions. This will be done separately for control at distance and near.

945 **7.7.2 Angle of Deviation**

946 At 3 months, a two-sided comparison of magnitude of the angle of deviation by PACT will be
 947 performed between treatment groups using an ANCOVA model, which adjusts for baseline
 948 PACT. The treatment group difference and an FDR-adjusted confidence interval will be
 949 calculated. The analysis will be completed separately at distance and at near.

950 Additionally, the proportion of participants with improvement of distance and near angle greater
 951 than the test/retest variability⁶³ will be compared between the treatment groups at 3 months using

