 952 a two-sided Barnard’s test with calculation of a two-sided FDR-adjusted confidence interval on
 953 the difference in proportions.

954 **7.7.3 Level of Suppression**

955 The proportion with each level of suppression (negligible, mild, moderate, or dense) will be
 956 compared between treatment groups at 3 months using an exact Wilcoxon rank sum test.

957 **7.7.4 Proportion with Anomalous Retinal Correspondence**

958 For those able to perform the test, the proportions of normal versus anomalous retinal
 959 correspondence will be compared between treatment groups at 3 months using a two-sided
 960 Barnard’s test for the difference in proportions.

961 **7.7.5 Convergence and Divergence Fusional Amplitudes**

962 The distribution of fusional convergence amplitude (blur point, break point, and recovery) and
 963 fusional divergence amplitude (break point and recovery point) will be described and compared
 964 between treatment groups at 3 months using an exact Wilcoxon rank sum test. When no blur is
 965 reported for fusion convergence, the break point will be used for analysis.

966 **7.7.6 IXT Symptom Survey Score**

967 The IXT Symptom Survey will be completed by children at the enrollment and 3-month exams.
 968 The distribution for each individual item (‘Never’, ‘Sometimes’, ‘All the Time’) will be tabulated
 969 for each treatment group within subgroups defined by age 5 to 9 years (all items) and age <5
 970 years for the single diplopia question.

971 **7.7.7 PedEyeQ Score**

972 The PedEyeQ consists of 3 components: child, proxy, and parent. After applying existing Rasch
 973 scoring,⁶¹ the average score for each of the domains within the three components will be
 974 compared between treatment groups at 3 months using an ANCOVA model, which adjusts for
 975 baseline PedEyeQ score. The treatment group difference and an FDR-adjusted confidence
 976 interval will be calculated.

977 **7.7.8 Binocular Diplopia by Parental Report**

978 The proportion of binocular diplopia at 3 months with a frequency of “more than 2 times per
 979 day” over the last week at distance or near, by parental report will be compared treatment groups
 980 at 3 months using a two-sided Barnard’s test.

981

982 **7.8 Exploratory Analyses**

983 Exploratory analyses described below will use observed data only. Point estimates and 95% CIs
984 will be reported for each outcome with no adjustment for multiplicity.

985 **7.8.1 Actual Patch Wear Time**

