3.3 Level of Suppression

- The proportion with each level of suppression (negligible, mild, moderate, or dense, as indicated on the
- completed follow-up worksheet) by treatment group at 3 months will be tabulated. The median and
- interquartile range for each group will be calculated and the distributions of suppression levels compared

between treatment groups at 3 months using the exact non-parametric Wilcoxon rank-sum test and twosample Hodges-Lehmann estimator.

4 Exploratory Analyses

Exploratory analyses will describe the distribution of the outcome, or change in outcome from baseline, within each treatment group and estimate treatment group differences and 95% confidence intervals (CIs), unless specified otherwise, with the purpose of identifying hypotheses for further study. All exploratory analyses will use observed data only without imputation for missing data. Only visits occurring within the analysis window will be included. As these are exploratory analyses, no adjustment for multiplicity will be made to confidence intervals and no p-values will be reported.

Continuous outcomes will be described using mean, standard deviation, and 95% CIs. Median and interquartile range (IQR) will also be reported if the outcome distribution is asymmetric. Treatment group differences and 95% CIs will be estimated using an ANCOVA model with adjustment for baseline level of the outcome. ANCOVA is relatively robust to violations of normality and homoscedasticity⁴; however, if ANCOVA model estimation of treatment group differences is of questionable validity due to violation of normality or other assumptions, actions to mitigate the violation will be undertaken. For example, for homoscedasticity violations, an ANCOVA model allowing the treatment groups to have different variances may be used and/or large outliers may be winsorized to the 5th and 95th percentiles of the overall outcome distribution (with treatment groups combined). In cases where winsorization of outliers is used, descriptive statistics for the treatment groups will be based on the outcome distribution after winsorization, and winsorized values will be noted in table/figure footnotes. Results of mitigated and original analyses will be compared for consistency, and results of both analyses reported if there are substantial differences.

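### Optional gain, not an error: the suppression comparison leaves the enrollment grade unused, and adjusting for it could add about 3 to 6 points of power if suppression tracks as distance control did

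*SAP*

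**What the plan says.** SAP 3.3 tabulates the four suppression levels and compares them "between treatment groups at 3 months using the exact non-parametric Wilcoxon rank-sum test and twosample Hodges-Lehmann estimator". Protocol 7.7.3 agrees: the levels are "compared between treatment groups at 3 months using an exact Wilcoxon rank sum test". Neither uses a baseline value.

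The baseline value exists. Protocol 2.4, item 13, lists among the enrollment procedures "Suppression: Assessment of suppression at distance (6 meters) using the Office Suppression" Test, and protocol 4.1, item 5, says that this test "grades the level of suppression while tropic on a 4-level scale". The same test is repeated at 3 months (protocol 3.4, item 13).

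Suppression sits in the SAP section 3 family, where the false discovery rate is held at 5% and only observed data are used. Protocol 7.7 adds that, unless otherwise specified, an "estimate of difference between the groups will be reported at each timepoint along with an" FDR-adjusted confidence interval and p-value.

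**The concern.** A comparison of 3-month grades alone leaves the differences that children already had at enrollment in the error term. If the grade is at all stable over 3 months, the enrollment grade explains part of that variation, and adjusting for it gives a more sensitive test from data already collected. The SAP does this for mean near control (3.1) and PACT angle (3.2).

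Suppression is a natural place to want the extra sensitivity. Protocol 1.4 describes patching as anti-suppression therapy with few data showing that suppression changes, and protocol 1.7 names evidence on suppression as something the study should provide. Yet the comparison has about 34 children per arm, no stated power, and shares an FDR family with seven others. What is at stake is a few points of power on one secondary outcome.

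**Working it through.** **Which correlation to assume.** The documents give none for suppression. The nearest analogue is distance control in the earlier trial (protocol 7.3, Table 1). With SDs at baseline (b), 3 months (f) and of change (c), r = (b² + f² − c²)/(2bf).

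- Observation (1.01, 1.35, 1.23): (1.0201 + 1.8225 − 1.5129)/2.727 = 0.488.
- Part-time patching (1.00, 1.23, 1.38): (1.0000 + 1.5129 − 1.9044)/2.46 = 0.247.

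**Check against the protocol's own figure.** The correlation of baseline with improvement is (b − r·f)/c.

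- Observation: (1.01 − 0.488 × 1.35)/1.23 = 0.286.
- Patching: (1.00 − 0.247 × 1.23)/1.38 = 0.504.
- Weighted by n: (131 × 0.286 + 116 × 0.504)/247 = 0.388.

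The protocol states that the correlation between baseline distance control and "change from baseline after 3 months was R=0.39 (95% CI, 0.27 to 0.48"), so the derivation reproduces it. Table 1's 95% limits for the SD of change (1.09 to 1.40 and 1.22 to 1.59) give r from 0.32 to 0.61 under observation and from −0.01 to 0.42 under patching.

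**Rough size by normal theory.** Adjustment multiplies the variance by 1 − r². At r = 0.38 it falls by 14.4%. Power becomes Φ((1.96 + z)/√(1 − r²) − 1.96), where z is the normal quantile of the unadjusted power. This gives 80% → 85.7% and 90% → 93.9%. It treats the outcome as continuous, so it is only a guide.

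**Simulation on a 4-level grade.** Assumptions: 34 per arm, latent-normal grades cut at −1.0, −0.2 and 0.6 (balanced), two-sided 5% before any FDR step, 6,000 trials per setting. The Wilcoxon test is compared with rank ANCOVA on the enrollment grade (permutation-type test, normal approximation). The 0.55/0.29 rows set the latent correlations so that the grades themselves correlate at about 0.49/0.25.

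| Latent r, observation/patching | Shift | Wilcoxon | Adjusted | Gain |
|---|---|---|---|---|
| 0.49/0.25 | 0.7 SD | 74.7% | 79.4% | +4.7 |
| 0.55/0.29 | 0.7 SD | 75.2% | 80.6% | +5.4 |
| 0.49/0.25 | 0.5 SD | 47.7% | 51.7% | +4.0 |
| 0.55/0.29 | 0.5 SD | 48.1% | 52.3% | +4.2 |
| 0.5/0.5 | 0.7 SD | 74.9% | 82.5% | +7.6 |
| 0.5/0.5 | 0.5 SD | 47.4% | 54.9% | +7.5 |
| 0/0 | 0.7 SD | 75.2% | 74.9% | −0.3 |
| 0/0 | 0.5 SD | 46.6% | 46.1% | −0.5 |

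Null rejection for the adjusted test was 4.2 to 5.5%. A second run of the analogue case gave 74.8 → 79.2% and 75.7 → 80.6% at 0.7 SD, and 47.2 → 50.6% and 46.7 → 52.4% at 0.5 SD. Across both runs the gain is +3.4 to +5.7 points.

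**Sensitivity.**
- *Table 1 limits.* A proportional-odds permutation test (rank ANCOVA stayed within 0.7 point of it) gave, at 0.7 SD, 75.3 → 75.8% for r of 0.32/−0.01 and 74.1 → 84.0% for 0.61/0.42. At 0.5 SD it gave 46.6 → 47.9% and 47.0 → 55.9%.
- *Skewed grades, same analogue.* Rank ANCOVA gained about 1.5 to 3 points. The proportional-odds test gained 3.8 and 4.5 with two skewed sets of cuts.
- *Patched-arm r of 0.* About +1 to +2 points.
- *FDR threshold.* I count eight comparisons in SAP 3: near control (1), two-point improvement at distance and near (2), PACT angle (2), PACT improvement beyond retest (2) and suppression (1). The strictest first-stage step is 0.05/1.05/8 = 0.006. There the proportional-odds test gained 3.2 to 8.0 points (18.7 → 21.9% up to 42.8 → 50.8%).

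**In children.** At 0.7 SD, Wilcoxon power was 74.2% at 34 per arm and 81.3% at 40, or (81.3 − 74.2)/6 = 1.18 points per child per arm. A gain of 4.7 points is worth about 4.7/1.18 = 4 more children per arm.

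**The case against.** The strongest objection is that the size rests on a borrowed correlation. Distance control is a different measure, scored once per visit in the earlier trial, in children selected for scores of 2 or more. The patching value comes from 3 hours a day. If full-time patching acts by reducing suppression, tracking in that arm could be weaker. The 3-month grader may also differ: because the enrolling "investigator will be unmasked to treatment group, they will not be allowed to serve as their own" masked examiner, agreement between visits may be lower. All of this stands, which is why the range matters more than any single figure.

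A second objection is that the planned test is exact, light on assumptions and agreed between the documents, so a heavier model would be a poor exchange. This stands against a proportional-odds model with its own interval and rules. It has little force against rank ANCOVA with a permutation p-value, which captures nearly all the gain.

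A third is that suppression is graded while tropic, so some children may have no grade, perhaps unevenly by arm. That affects the planned test as well. It is a reason to report the missing counts.

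A reader might infer that the SAP contradicts itself because near control and PACT angle are baseline-adjusted. The documents do not support that: fusional amplitudes (SAP 4.2) are also compared at 3 months without adjustment, and SAP 3.3 matches protocol 7.7.3.

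**Conclusion.** The omission is real, and the improvement is optional. The Wilcoxon test is valid under randomization, and the primary analysis and sample size are unaffected.

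If suppression tracks as distance control did (r of about 0.49 and 0.25), baseline adjustment adds about 3 to 6 points of power at 34 per arm with balanced grades, and about 1.5 to 4 with skewed grades. Over plausible correlations the range is about 0 to +10, with a loss of up to about 1 point when r is near zero. These figures assume a latent-normal grade, shifts of 0.5 to 0.7 SD and a grade for every child. None of these assumptions is stated in the documents. A reader might take the middle of the range as an established gain; without a correlation for suppression, it is only one assumed case.

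**What to change.** Only if treatment-group data have not been seen (SAP version 1.2 is dated 6 May 2025, and the documents do not say):

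1. In SAP 3.3, take the FDR-controlled p-value from a rank ANCOVA of the 3-month grade on the enrollment grade. Permute treatment labels within the three randomization strata, defined in protocol 2.5 by mean distance control "score at enrollment (2 to <3, 3 to <4, 4 to 5"). State the number of permutations and the seed.
2. Keep the table, the Hodges-Lehmann estimate and the exact Wilcoxon test as descriptive or supportive results.
3. Use children with both grades observed, so that the observed-data rule in SAP 3 stands. Report by arm how many lack a grade at each visit.
4. Change protocol 7.7.3 to match, which needs IRB approval (protocol 9.2), or record the SAP change as a documented refinement. Protocol 7.7 leaves further detail on secondary analyses to the SAP.

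If data have been seen, leave the planned test in place and report the adjusted test as a labelled supportive analysis.

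The cost is a few lines of text and code, with no new data. There are three downsides:
- Power falls slightly if r is near zero.
- Children without an enrollment grade drop out of the adjusted test. If 5% were missing (an assumption), that is 34 × 0.05 = 1.7 per arm, or about 1.7 × 1.18 = 2 points, a sizeable part of the gain. Check completeness of the enrollment grade, pooled over arms, before adopting the change.
- The p-value no longer pairs exactly with the unadjusted Hodges-Lehmann estimate. That pairing is already loose on integer grades: at 0.7 SD with skewed levels, the estimate was 0 in 23 to 33% of significant Wilcoxon tests.
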